## 1. Research plan.

**1.A. Background** Chronic obstructive pulmonary disease (COPD) currently afflicts 24 million US residents and is the 3th leading cause of death in the United States {{164 Anonymous 2001; 368 Mannino,D.M. 1997}}. Each year, 150,000 patients die from

COPD in the U.S. or about one patient every 4 minutes. Health care costs for COPD patients in the US is approximately \$6.5 billion/ year, but its indirect costs probably double the costs of care when taking into account lost productivity and caretaker expenses {{465 Sin,D.D. 2002; 378 Miravitlles,M. 2002; 473 Sullivan,S.D. 2000}}. COPD exacerbations add considerably to that burden because they: (1) cause frequent hospital admissions and relapses or readmissions, (2) contribute directly to the death of many patients, either during hospitalization or shortly thereafter, (3) cause patients significant stress, prolonged physical discomfort, disability and dramatically reduced quality of life, (4) consume the majority of the resources available to manage this chronic condition. (5) frequently progress to a severe stage warranting hospitalization before any abortive treatment is instituted, and (6) may hasten the progressive loss of lung function, a steady decline that is a cardinal feature of COPD itself {{280 Garcia-Aymerich, J. 2003; 452 Seemungal, T.A. 1998}. Two studies have estimated that acute exacerbations of COPD (AECOPD) account for 31 to 68% of the total costs of COPD care in the US {{378 Miravitles.M. 2002: 294 Halpern.M.T. 2003}. Hence treatment that could prevent or ameliorate frequent or severe AECOPD could significantly lessen COPD morbidity and mortality as well as costs.

Hospitalized exacerbations are particularly relevant in COPD patients. Hospitalized exacerbations result in a profound impact on patient survival, function, symptoms and health status as well as costs Hospitalizations accounted for a significant component of COPD related costs. Re-hospitalization in COPD is frequent and associated with a particularly negative impact. Patients discharged from the hospital after a COPD exacerbation have a high mortality and are frequently readmitted with recurrent exacerbations. The cause of these high rates of readmission is not well understood. Although a number of pharmacologic and behavioral interventions have been used to decrease exacerbations in COPD, it is not clear that these same interventions are successful in reducing hospital admission rates or re-admission rates. Except for the use of noninvasive ventilation in patients that present in acute respiratory failure during COPD hospitalization, no new therapies have been discovered in the last 3 decades. Hence, investigations of new therapies to treat COPD patients who are hospitalized with a severe exacerbation are desperately needed.

**1. B. Why survival and readmission rates are desirable outcomes for studying** interventions in hospitalized acute COPD exacerbations. The Pennsylvania Cost Containment Council (PHC4) reported in 2012 using a statewide database of several million Pennsylvania residents hospitalized in FY 2009 that COPD was the third most common cause of readmission within the year post discharge (25.7%) and that 9.5% of patients were readmitted more than once in the year following hospitalization. In fact, 4.2 % of the COPD patients were readmitted 3+ times in the year post hospitalization. (Figure 1).

[figure not shown]
Others have reported similarly high readmission rates following COPD hospitalization as enumerated in the Table 1:

Citation	Study Structure	30 day readmission	60 day readmission	90 day readmission
Lau et al 2001	Retrospective	~15%	~25%	~30%
Almagro et al 2002	Prospective	~5%	~10%	~13%
Roberts et al 2002	Retrospective	34%	NA	NA
		14% respiratory		
Westert et al 2002	Retrospective	USA 4.1-1.3%	NA	NA
		Europe 8.5-13.4%		
Almagro et al 2005	Prospective	16%	~25%	35%
Schiotz et al 2011	Retrospective	21.4 in 2007	NA	NA
Nansupawat et al 2012	Retrospective	13.6%	NA	NA
Moullec et al 2012	Prospective	~20%	~30%	~40%

## Table1. Readmission rates following COPD Hospitalization

Dinesen et al 2012	Prospective	~5%	~6%	~10%

The rate of 30 day readmissions in these reports varies from 5-34% with the majority of studies suggesting that approximately 15% suffer such an event in that time frame. This readmission rate increases further by 60 days (6-30%) and 90 days (10-40%).Data from the AHRQ using the HCUP database found that 20.5% of U.S. COPD patients were readmitted within 30 days and that 85% of these included COPD as the primary or secondary diagnosis).{{1159 Elixhauser,A. 2011}} A summary of published literature suggests that readmissions are frequently seen in this population.

Survival is another extremely relevant endpoint to study the effect of an intervention during COPD hospitalization. The Study to Understand Prognosis and Preferences for Outcomes and Rates of Treatment (SUPPORT enrolled patients admitted with COPD exacerbations and reported an in-hospital mortality of 11% in patients presenting with acute hypercapneic respiratory failure.{{1152 Connors,A.F.,Jr 1996}} The 180 day mortality was 33% and the 2-year mortality was 49%. Several

other studies have reported in-hospital mortality rates of 11-24% and 22-35% after one and two year's follow-up respectively (Figure 2). The 2010 PHC4 dataset reports the average inpatient mortality rate for COPD readmissions to be 3.9%, but ranges from non-complicated readmission mortality rates of 1.45 % to 5.0% if pneumonia is the cause of readmission in a patient initially admitted with COPD or even higher at 11.6% mortality if respiratory failure is the cause for readmission.

These data demonstrate that readmission and survival following COPD hospitalization are clinical relevant and meaningful endpoints that occur with increased frequency following the index hospitalization.

## 2. Research plan.

**2.A.** What drives the increased morbidity and mortality associated with hospitalized acute COPD exacerbations? The inflammation associated with COPD, especially the heightened inflammation that occurs during hospitalized AECOPD, may contribute to the higher rates of morbidity and mortality. Data that demonstrates that inflammation is heightened in stable COPD and especially during an exacerbation is robust and identifies multiple potential responsible inflammatory cell lines, chemokines and cytokines. Elevations in serum systemic inflammatory mediators correlate with the

presence or worsening of COPD. A meta-analysis of 14 studies with data on systemic inflammation markers (e.g., CRP, fibrinogen, IL-6) and COPD confirmed the association between reduced lung function and systemic inflammation {{278 Gan, W.Q. 2004}}. COPD exacerbations are linked to increased signals of systemic oxidative stress (e.g., higher serum lipid peroxidation byproducts; up-regulated CD11/CD18 neutrophil adhesion molecules; increased cytochrome oxidase activity in lymphocytes and skeletal muscle {{420 Rahman, I. 1996; 395 Noguera, A. 1998; 442 Sauleda, J. 1998}}. CRP can induce pro-inflammatory cytokine and chemokine expression and the up-regulation of adhesion molecules that may promote lung inflammation {{411 Pepys, M.B. 2003}}. CRP levels appear to correlate with the future risk of morbidity and mortality in COPD {{364 Man, S.F. 2006; 239 Dahl, M. 2007}. One group has reported that CRP is the biomarker that correlates best with the presence of a symptomatic exacerbation {{311 Hurst, J.R. 2006}. Acute exacerbations that are slow to resolve are associated with higher CRP levels. A large population based study confirmed a significantly increased risk of hospitalization in COPD patients with CRP levels above 3 mg/L {{412 Perera, W.R. 2007; 239 Dahl,M. 2007}}.

IL-6 is also considered part of the acute phase response and appears to be a potent inducer of CRP expression in the liver. IL-6 levels are increased in sputum, bronchoalveolar lavage fluid and blood in COPD and are even further increased during periods of exacerbation {{364 Man,S.F. 2006; 198 Bhowmik,A. 2000; 207 Bucchioni,E. 2003; 518 Wedzicha,J.A. 2000}}. As with CRP, elevated IL-6 levels are associated with decreases in pulmonary function and a higher number of exacerbations per year {{260 Donaldson,G.C. 2005; 517 Wedzicha,J.A. 2002}}.

Additional pro-inflammatory mediators may be implicated based on published evidence of a correlation in the elevations in these biomarkers with disease severity {{208 Calikoglu, M. 2004;311 Hurst, J.R. 2006; 518 Wedzicha, J.A. 2000; 205 Bozinovski, S. 2008 }}. Activated bronchial epithelial cells, macrophages and neutrophils produce IL-8 {{471 Spruit, M.A. 2003;518 Wedzicha, J.A. 2000; 205 Bozinovski, S. 2008; }}, which is a potent chemoattractant for neutrophils and monocytes and likely contributes to the mobilization of these cells into the lung. IL-8 levels are increased in the sputum of COPD patients and correlate with the intensity of the neutrophilic response. TNF- $\alpha$  is a critical pro-inflammatory molecule that is believed to primarily work by inducing a broad spectrum of pro-inflammatory cytokines, chemokines, proteases and adhesion molecules by activating transcriptional activating factor p38 mitogen-activated protein kinases and nuclear factor (NF)-kB in macrophages and epithelial cells {{205 Bozinovski, S. 2008;471 Spruit, M.A. 2003; 518 Wedzicha, J.A. 2000; 529 Yamamoto, C. 1997; 235 Crooks, S.W. 2000; 288 Gompertz, S. 2001 }}. IL-15 is important for the function of CD8 positive cells {{346 Ku,C.C. 2000; }}, an important inflammatory cell population in the lung in COPD. IL-17 is now understood to be a very critical proinflammatory cytokine, produced by highly inflammatory CD4 and CD8 T cells, which promotes the recruitment of numerous inflammatory leukocyte populations, and induces the expression of mucin by lung epithelial cells { 538 Oda, N. 2005; 539 Chen, Y. 2003; 540 Hashimoto,K. 2004; }}. IL-18 is produced by inflammatory macrophages, and induces the production of chemoattractant factors including IL-8 (which attracts neutrophils and monocytes/macrophages to the site of inflammation){{541 Imaoka,H. 2008;542 Petersen, A.M. 2007; 543 Hoshino, T. 2007; }}, and the expression of additional pro-inflammatory mediators such as GM-CSF and IL-6. Pulmonary and activation-regulated chemokine (PARC/CCL18) is produced at high levels in the lung,

and is up-regulated with activation of alveolar macrophages, and strongly recruits both CD4 and CD8 T cells to sites of inflammation. MPIF-1 (CCL23) is produced by activated macrophages, and acts to attract both monocytes and T cells to inflamed tissue, including the lung. Eotaxin-2 (CCL24) is produced in part by alveolar epithelial cells in response to pro-inflammatory cytokines such as TNF $\alpha$ , and may reflect the degree of both the local inflammatory status, and the state of epithelial cell activation in the diseased lung. Surfactant protein D (SP-D) is a large hydrophilic protein that is a member of the collagen containing C-type lectins or collectins and plays a role in protecting against viral infection, in clearing bacteria, fungi and apoptotic cells, and in resolving inflammation{{337 Kierstein,S. 2006;342 Kishore,U. 2006; }}. Serum SP-D is elevated in COPD compared to current and former smokers with airflow limitation and that serum SP-D levels greater than the 95th percentile of non-smokers are at increased risk for exacerbation in the subsequent 12 months {{357 Lomas,D.A. 2009; }}.

Inflammation associated with COPD exacerbation may be responsible for some of the non-pulmonary manifestations of an acute exacerbation and may explain some of the morbidity and mortality associated with these events. Cardiac events (e.g., arrhythmias, acute myocardial infarction, and unstable angina) are a major cause of morbidity and mortality in COPD and vascular dysfunction is commonly observed in even stable COPD {{374 McAllister, D.A. 2007; 532 Zureik, M. 2001; 483 Tillie-Leblond, I. 2006; 319 Janssens, J.P. 2001; 237 Curkendall, S.M. 2006; 297 Hansell, A.L. 2003; 262 Engstrom, G. 2002; 263 Engstrom, G. 2001; 372 Marcus, E.B. 1989; 413 Persson, C. 1986; 274 Friedman, G.D. 1976}. Donaldson et al has recently reported that acute myocardial infarctions and cerebrovascular accidents more likely to occur 1-2 months following an acute exacerbation and correlate with increases in IL-6 and fibrinogen.{{1163 Donaldson,G.C. 2010}} Brekke and colleagues have shown that elevations of cardiac specific troponin are frequently present in acute COPD exacerbations and levels inversely correlate with long-term survival. {{1162 Brekke, P.H. 2009}Flow mediated dilation (e.g., measure of vascular function) is impaired in stable COPD outpatients and is more impaired with worsened airflow obstruction or increased systemic inflammation {{536 Eickhoff, P. 2008; 187 Barr, R.Graham 2007; 537 Moro, L. 2008}. We have recently reported that during an acute hospitalized exacerbation, COPD patients have markedly impaired flow mediated dilation that is worse than that reported in other disorders associated with severe systemic inflammation such as rheumatoid arthritis. {{1153 Marchetti, N. 2011}}

Increased thrombotic events are also found in COPD and those experiencing an acute hospitalized exacerbation.{{1144 Rizkallah,J. 2009}} An autopsy study in 46 patients who died within 24 hours of AECOPD hospitalization suggested cause of death as CHF in 37% and VTE in 21% {{534 Zvezdin,B. 2009}}. VTE occurs 5 times more commonly in COPD and can be an unexpected cause of AECOPD in up to 25% of hospitalized patients {{483 Tillie-Leblond,I. 2006}}. We have shown that COPD patients have increased levels of procoagulant factor VII levels and thrombin anti-thrombin products that indicate a heightened state of thrombosis.{{361 Vaidyula,V.R. 2009}} Others have reported denser fibrin complexes in COPD compared to age-matched controls. {{1161 Undas,A. 2009}} COPD, cardiac disease and VTE are closely coupled by shared risk factors (older age and smoking) as well as common pathophysiological features (presence of acute inflammation). Inflammation is present in all COPD stages and vTE (IL-6, IL1 - $\beta$ , TNF- $\alpha$ , MMP-9, MCP-1 and CRP) are also elevated in COPD{{278

Gan,W.Q. 2004; 260 Donaldson,G.C. 2005; 455 Shapiro,S.D. 2001; 426 Retamales,I. 2001; 434 Rutter,M.K. 2004; 340 Kinlay,S. 2003; 247 de Torres,J.P. 2008; 219 Churg,A. 2004; 528 Yamada,S. 2001}

As described below, therapies such as PDE-4 inhibitors like roflumilast that can decrease lung and systemic inflammation may be useful in decreasing the acute pulmonary as well as non-pulmonary morbidity and mortality that is associated with severe COPD exacerbations that require hospitalization.

#### 2.B. PDE-4 Inhibitors and specifically Roflumilast may have beneficial antiinflammatory effects in the lung that may be relevant for COPD patients during an acute severe hospitalized exacerbation.

PDE-4 inhibition has consistently demonstrated a reduction in activity of several proinflammatory cells that are involved in the pathophysiology of COPD. There is some evidence that PDE-4 inhibition can suppress pro-inflammatory cell recruitment and chemokine and cytokine production.

[figure not shown]
Clinical data has supported the notion that roflumilast via its PDE-4 inhibition pathway may have important effects on decreasing exacerbation in COPD. Calverley has shown in COPD patients with moderate to severe disease that roflumilast for one year results in a small but significant improvement in FEV1 and moderate reduction in exacerbation rate {{ Calverley, AJRCCM, 2007}} Fabbri et al has reported the effects of roflumilast vs. placebo in addition to salmeterol or tiotropium and found that roflumilast use was associated with sustained improvements in FEV1 and reductions in exacerbations rates.{{ Fabbri, 2009, Lancet}} Calverley again reported in two additional studies that roflumilast use compared to placebo was associated with significant but modest increase in FEV1, but more impressively, substantial reduction in both moderate and severe exacerbations. {{Calverley, Lancet, 2009}}. These data highlight the potential importance that roflumilast may have on decreasing the intensity of symptoms around the time of an acute severe exacerbation that requires hospitalization and its potential benefit on reducing mortality and the need for readmission.

## 3. Study design

3. A. Specific Aims: In this **pilot** proposal, we will test the feasibility of roflumilast to decrease all cause readmission and mortality 180 days after hospitalization for acute COPD exacerbation. We propose to conduct this study in 100 patients at three centers to assess the tolerance and treatment effect of roflumilast in order to power an appropriate definitive phase III multicenter trial.

Our ultimate specific aims in the **phase III trial** will be to assess: **1**) Primary aim: Evaluate the effects of roflumilast 500 ug daily in hospitalized AECOPD patients on time to all-cause mortality or re-hospitalization during the 180 days following randomization and; **2**) Secondary aims: Evaluate the effects roflumilast 500 ug daily in this population on the following outcomes: respiratory-related death or re-hospitalization during the 180 days following randomization; rate of death or readmission during the 30 days postdischarge; treatment failure (see definition below); change in health status, FEV1, and dyspnea during the 180 days following randomization; post-randomization ICU admission, need for non-invasive or invasive mechanical ventilation, and length of hospital stay during the index hospitalization and; 3) Other: Assess tolerance of roflumilast vs. placebo in hospitalized AECOPD

**3.B. Study Design and Synopsis:** Parallel-group, prospective, randomized, double blind, placebo-controlled trial of roflumilast 500 ug daily vs. placebo in approximately 100 hospitalized AECOPD patients (Figure 3). Both groups will receive GOLD guideline-recommended care.

## Outcomes:

In this pilot proposal, 100 patients at three centers will be evaluated to test the feasibility of conducting this study and to assess the treatment effect of roflumilast to be able to power an appropriate definitive phase III multicenter trial. Our ultimate aims of the phase III trial will be:

**1) Primary**: time to all-cause mortality or re-hospitalization during the 180 days postrandomization. **2) Secondary:** respiratory death or respiratory re-hospitalization during the 180 days post-randomization; rate of death or readmission during the 30 days postdischarge; treatment failure (see definition below); change in health status, FEV1, and dyspnea during the 180 days post-randomization; length of hospital stay during the index hospitalization. **3) Other: assess tolerance of roflumilast vs. placebo in hospitalized AECOPD.** 

[figure not shown]

Figure 4 shows the overall study design, proposed study measurements, and time points for assessment. Patients hospitalized with AECOPD will be eligible for enrollment during their hospitalization with treatment being started before discharge from the hospital.. Demographics, blood tests, health related quality of life, comorbidity (Deyo-Charlson index), post bronchodilator spirometry, vital signs, dyspnea measured by MMRC, SaO2 and amount of inspired O2 to maintain SaO2> 90% at rest, serum fibrinogen levels, HBA1c, Biomarkers and Genetics will be obtained after enrollment and then patients will be randomized to standard AECOPD care plus roflumilast 500 ug daily vs. placebo. Patients will begin roflumilast or placebo  $\leq$  12 hours of hospitalization for a total period of 180 days post enrollment. On discharge day (approximately day 3-4 after admission based on the recent COPD CRN zileuton study of hospitalized AECOPD), the measurements will be repeated as indicated (baseline measurements), with follow-up phone assessments at days 7, 30, 60, 90, 120 and 194 days post enrollment. An inperson clinical visit will be conducted at days 14 and 180 post randomization.

## 4. Methods:

**4. A. Study Population.** 100 AECOPD patients hospitalized at Temple University Hospital, Temple University Episcopal Hospital Campus, Jeanes Hospital and St Mary's Hospital.

**Inclusion Criteria.** Primary diagnosis of AECOPD defined as acute increase in dyspnea, sputum volume, and/or sputum purulence without other identified cause; consent obtained and treatment started before discharge from the hospital ; patient age >40, < 80 years old; cigarette smoking  $\geq$  10 pack-years; informed written consent.

**Exclusion Criteria.** Prior diagnosis or high suspicion for asthma based on investigator judgment; pulmonary edema, pneumonia, interstitial lung disease or significant Version 04.13.2015

bronchiectasis based on admission chest x-ray; intubated and mechanically ventilated at the time of evaluation; active liver disease, or transaminase elevations ( $\geq$  3xULN); history of alcoholism or heavy ethanol use; history of suicidal behavior  $\leq$  2 years or suicidal ideation  $\leq$  6 months prior to enrollment; pregnant or lactating females. Those on the following excluded medications: P450 inducers (e.g., rifampicin, phenobarbital, carbamazepine, and phenytoin) and CYP3A4 inhibitors or dual inhibitors that inhibit both CYP3A4 and CYP1A2 simultaneously (e.g., erythromycin, ketoconazole, fluvoxamine, enoxacin, cimetidine.

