## 4. B. Study Procedure

Study will begin before patient's discharge from the hospital and last for 194 days.

Baseline: Will occur during the duration of admission stay in the hospital. Patients will have a medical history taken as well as smoking history. Patients will also be given a physical exam including vital signs. A spirometry test will also be performed. Women with the potential to become pregnant will be given a pregnancy test. Data will also be collected in regards to dyspnea scales, Deyo-Charlson index, and GOLD classification. Patients will complete a Columbia Suicide Severity Rating Scale to exclude patients with a history of suicidal behavior  $\leq 2$  years or suicidal ideation  $\leq 6$  months prior to enrollment Randomization: Patients who are eligible to enroll in this study will be randomized to one of two treatment groups. Randomization will be done using a randomized block design stratified by treatment center. One group will receive rollumilast 500 mcg (Daliresp®) and the other will receive a placebo tablet. Patients will begin one of these treatment arms prior to hospital discharge for a total period of 180 days post enrollment.

Day of hospital discharge: A spirometry test will be performed and an adverse event assessment will be completed.

Day 7: Phone Visit. Data to be collected includes: interim history, adverse events assessments, vital status, and exacerbation history. During this telephone visit the study doctor or nurse coordinator will ask how the patient is feeling and if they have needed to visit the doctor or go to the emergency room or hospital since the last time they were contacted. They will be asked how well they are tolerating the study drug.

Day 14: Clinic Visit. At this visit vital signs, C-SSRS test, interim history, adverse event assessment, vital status, and exacerbation history will be recorded. The following questionnaires will given: EQ-5D, the St. George's Respiratory Questionnaire (SGRQ), and the Modified Medical Research Council dyspnea score (MMRC).

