Days 30, 60, 90, & 120: Phone Visit. Data to be collected includes: interim history, adverse events assessments, vital status, and exacerbation history. During each of these telephone visits the study doctor or nurse coordinator will ask how the patient is feeling and if they have needed to visit the doctor or go to the emergency room or hospital since the last time they were contacted. They will be asked how well they are tolerating the study drug.

Day 180: Clinic Visit. At this visit vital signs, C-SSRS test, interim history, adverse event assessment, vital status, and exacerbation history will be recorded. A spirometry test will be performed as well during this visit. The following questionnaires will given: EQ-5D, the St. George's Respiratory Questionnaire (SGRQ), and the Modified Medical Research Council dyspnea score (MMRC).

Day 194: Phone Visit. This phone call covers the wash out period for the study treatments. Data to be collected includes: interim history, adverse events assessments, vital status, and exacerbation history. During this telephone visits the study doctor or nurse coordinator will ask how the patient is feeling and if they have needed to visit the doctor or go to the emergency room or hospital since the last time they were contacted.

**4. C. Demographics and Medical History**. Age, gender, body mass index (BMI), smoking history (debut, amount, duration), presence of comorbidities, current medical therapy (bronchodilators, steroids, oxygen), history of pulmonary rehabilitation, influenza and pneumococcal vaccination, emergency room visits and hospitalizations during last year, number of prior exacerbations in prior year, history of coronary artery disease, stroke, transient ischemic attacks, and peripheral vascular disease. The Deyo-Charlson index, a standard and validated measure of co-morbidity {{252 Deyo,R.A. 1992; }}, will be used to assess the impact of other chronic illnesses on outcome.

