## 4. N. Contraindications and side effects to the use of Roflumilast.

**1. Contraindications**: Roflumilast in contraindicated in patients with moderate or severe liver impairment (Child-Pugh class B and C)

2. Side effects: Adverse events experienced by > 3% of patients in clinical trials of roflumilast included diarrhea (9.5%), weight loss (7.5%), nausea (4.7%), headache (4.4%) and back pain (3.2%). Patients discontinued therapy due to adverse effects more frequently with roflumilast (14.8%) compared to placebo (9.9%). Diarrhea and nausea were the most common adverse reactions leading to drug discontinuation in prior trials. Serious adverse events that occurred more frequently with roflumilast compared to placebo included diarrhea, atrial fibrillation, lung cancer, prostate cancer, acute pancreatitis acute renal failure. Less common adverse events, (1-2%) of patients that were more frequently reported with roflumilast use as compared to placebo included abdominal pain, anxiety, heartburn, depression, gastritis, rhinitis, sinusitis, muscle spasms, tremor, urinary tract infection, and vomiting. Roflumilast carries a warning for increased psychiatric adverse events and suicidality. Patient should be monitored for changes in mood including worsening insomnia, anxiety or depression or suicidal ideations. Roflumilast also carries a warning for weight loss. 20% of patients may experience moderate weight loss between 5 to 10% of ideal body weight compared to 7% with placebo.

Roflumilast side effects reported in  $\ge 2\%$  of recipients from 8 clinical trials as listed in the manufacturer's package insert are listed in the table below.

Treated with Roflumilast 500 mcg daily and Greater Than Placebo Treatment		
Adverse Reactions	Roflumilast	Placebo
(Preferred Term)	(N=4438)	(N=4192)
	n (%)	n (%)
Diarrhea	420 (9.5)	113 (2.7)
Weight decreased	331 (7.5)	89 (2.1)
Nausea	209 (4.7)	60 (1.4)
Headache	195 (4.4)	87 (2.1)
Back pain	142 (3.2)	92 (2.2)
Influenza	124 (2.8)	112 (2.7)
Insomnia	105 (2.4)	41 (1.0)
Dizziness	92 (2.1)	45 (1.1)

Decreased appetite	91 (2.1)	15 (0.4)

Other side effects reported in 1- 2% of recipients include: Gastrointestinal disorders (abdominal pain, dyspepsia, gastritis, vomiting); Infections and infestations (rhinitis, sinusitis, urinary tract infection); Musculoskeletal and connective tissue disorders (muscle spasms); Nervous system disorders (tremor); and Psychiatric disorders (anxiety, depression).

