## 4. O. Drug Interactions with Roflumilast.

## 1. Drugs That Induce Cytochrome P450 (CYP) Enzymes

Strong cytochrome P450 enzyme inducers decrease systemic exposure to roflumilast and may reduce the therapeutic effectiveness of roflumilast. Therefore the use of strong cytochrome P450 inducers (e.g., rifampicin, phenobarbital, carbamazepine, and phenytoin) with roflumilast is not recommended and these medications will be excluded from use in the trial.

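### Minor, patient safety only: the liver exclusion in 4.A does not match the protocol's one stated contraindication in 4.N (Child-Pugh B and C), and no readable text applies that contraindication at entry

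*Combined protocol and SAP*

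**What the plan says.** Section 4.A (Study Population, Exclusion Criteria) excludes "active liver disease, or transaminase elevations", with the enzyme threshold set at 3 times the upper limit of normal or more. It does not define *active*. The same list excludes a "history of alcoholism or heavy ethanol use", with no time limit.

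Section 4.N (Contraindications and side effects) has one entry under contraindications. It states that roflumilast is "contraindicated in patients with moderate or severe liver impairment (Child-Pugh class B and C").

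Section 4.B (Baseline) says "Patients will have a medical history taken as well as smoking history", and adds a physical examination. Section 4.C collects comorbidities and says of the Deyo-Charlson index that it "will be used to assess the impact of other chronic illnesses on outcome". The Outcomes text in section 3 lists blood tests, not itemised, among the measurements that "will be obtained after enrollment and then patients will be randomized to standard AECOPD care".

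**The concern.** A patient with a contraindication to the study drug should be kept out by the entry criteria, in the terms in which the contraindication is stated. Here the entry rule asks whether liver disease is active and how high the enzymes are, while the contraindication asks how impaired the liver is. A patient can meet the second description without clearly meeting the first.

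The stake is the safety of an individual patient. Someone in the gap who was assigned to the active arm would be planned for 500 mcg daily for up to 180 days of a drug that the same protocol says they should not take. In the readable visit schedule, the contacts between the day 14 and day 180 clinic visits are by telephone, so entry is the natural point to apply the restriction.

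**Working it through.** There is no plan figure to reproduce and no arithmetic to run. The check compares wording.

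**Step 1: is Child-Pugh class used anywhere at entry?** In the readable text it appears only in 4.N. The liver is mentioned in three places: the background on inflammatory markers in 2.A, the exclusion in 4.A and the contraindication in 4.N. None of these makes Child-Pugh class a condition of enrollment or randomization.

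**Step 2: does another baseline item apply it?** Sections 4.B and 4.C provide for history, examination and comorbidities. The only use stated for the comorbidity index is to study its bearing on outcome, not to decide eligibility.

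**Step 3: who, among class B or C patients, does 4.A keep out?** Take them in turn:

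| Class B or C patient | Result under 4.A as written |
|---|---|
| Transaminases at or above 3 times ULN | Excluded by the enzyme limb |
| History of alcoholism or heavy drinking, at any time | Excluded by the alcohol criterion |
| Neither of these, disease judged active | Excluded by the first limb, whatever the enzymes |
| Neither of these, disease not judged active | Not clearly excluded |

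The last row is the whole gap. It requires four things together: class B or C impairment, a cause other than alcohol, transaminases below the threshold, and a judgement that the disease is not active. For that patient the only barrier left is an investigator who turns to 4.N and acts on it.

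**Step 4: would closing the gap disturb the statistical plan?** Section 4.R.4 rests on 100 patients, 73 events, a hazard ratio of 1.654, a two-sided 10 percent level and 70 percent power. None of these inputs depends on the liver criterion, so an added exclusion changes none of them.

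**The case against.** The strongest reply is that the case is already covered. The first limb of the exclusion has no enzyme threshold, so low transaminases do not make a patient eligible. Most investigators would call moderate or severe impairment active liver disease. The alcohol criterion removes further patients, and 4.N sits in the same Methods section, so harm requires a physician to give a drug that the protocol itself calls contraindicated. On this view the change only tidies the drafting. Much of this stands, and it is why the point is minor. It does not remove the mismatch: the last group in the table depends on how an undefined word is read at several hospitals.

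Three stronger readings are tempting, and the documents support none of them.

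- *A reader might infer from 4.O that the contraindication was deliberately left out of the entry rules.* Section 4.O.1 says of strong P450 inducers that their use "is not recommended and these medications will be excluded from use in the trial", and 4.N has no such sentence. But 4.O.2, on CYP3A4 and dual inhibitors, has none either, and 4.A excludes those drugs all the same. The missing sentence in 4.N therefore proves nothing.
- *A reader might infer that sites screen only against the 4.A list.* No readable text says so. Section 4.H refers to exclusion criteria numbered 9a and 9b, and 4.A has no numbering. That may be wording carried in with the suicidality scale, but 4.A cannot be assumed to be the working checklist.
- *A reader might infer that the trial already collects the laboratory values needed for the score.* The blood tests are not itemised, they are described as obtained after enrollment, and Figure 4 is not visible. Nothing can be said about which liver tests the trial performs, or whether they are available at screening.

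**Conclusion.** The point holds as a minor mismatch between an entry rule and the drug's stated contraindication, bearing on patient safety only. Most class B or C patients would probably be kept out already. A patient with non-alcohol cirrhosis, transaminases below 3 times ULN and disease not judged active is not clearly excluded. The number affected cannot be estimated from the documents and may be zero, so no probability is given.

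A reader might go further and infer that contraindicated patients will be enrolled, or that the primary comparison is compromised. The documents do not support either: the gap needs several conditions at once and an investigator who does not act on 4.N, and nothing links it to the log-rank analysis or its sample size.

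The conclusion rests on two assumptions. The first is that class B or C impairment can coexist with transaminases below the 4.A threshold; the documents neither state nor deny this. The second is that the figure and pages not available for review contain no entry rule based on Child-Pugh class.

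**What to change.** Add Child-Pugh class B or C (moderate or severe hepatic impairment) to the exclusions in 4.A, beside the existing liver criteria. Assess it before randomization from the history, the examination and routine inpatient chart and laboratory data, and only in patients with a prior diagnosis or high suspicion of chronic liver disease in the investigator's judgement. Section 4.A already uses a trigger of this kind for asthma ("Prior diagnosis or high suspicion for asthma based on investigator judgment"), so the form is familiar, and other patients need no new screening procedure.

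The cost is one phrase in 4.A, an occasional extra screen failure, and a chart-based score for the few patients who meet the trigger. Because the trial's own blood tests are not itemised, the values for the score should come from routine care and should not be presumed to be in the study database.
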